*Primary objective(s):* To determine the feasibility of performing HIVM in patients with deep space solid tumors during standard course of surgical resection. A successful intravital microscopic observation will include the ability to complete each of the following:

1. Identify and measure vessels associated with tumor
2. Determine vessel density per 10x field
3. Visualize vital dyes within the vessels (fluorescein)
4. Calculate the blood flow velocity of the vessels and tissue penetration of fluorescein as a marker of vessel permeability.
5. Obtain these vessel parameters after administration of an IV fluid bolus and/or vasopressor administration (phenylephrine or vasopressin) during the normal course of the surgical resection.

*Secondary objective(s):*

1. Compare the microscopic observation of the tumor-associated vessels with normal tissue (e.g. peritoneal surface) in each individual subject.
2. Correlate the microscopic observations of the tumor-associated vessels with pathologic grade of tumor.
3. To correlate the microscopic observation of the microvasculature with tumor-specific and overall survival.

Study Design: This is a non-randomized, single center, study of HIVM observation in subjects with deep space solid tumors undergoing surgical resection.

All subjects will meet the inclusion and exclusion criteria prior to participation in this study. Standard evaluation by the Preoperative Anesthesia clinic at Mayo Clinic Florida may include additional testing such as EKG, chest x-ray, and/or pulmonary function tests.

The study will be performed in two parts. Part 1 will enroll 10 patients with an expected feasibility rate of 70%. Whereas the feasibility rate in primary melanoma was 90%, the expected feasibility rate for deep space tumors may be lower as the site is in an anatomically deeper location. If Part 1 is not met (i.e. in three or more patients), the primary objective would not be considered technically feasible, and then the study will be stopped. If Part 1 is fulfilled, then the study will continue with an additional 40 patients enrolled (total of 50 patients). Accrual is expected to take 2.5 years.

*Inclusion criteria:*

1. Age  $\geq$  18 years of age.
2. ECOG Performance Status of  $\leq 2$ .
3. Measurable tumor by direct visualization requiring surgical resection in the OR.

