4. Tumor types of origin include gastric, pancreatic, hepatobiliary, colorectal, and sarcoma. Tumors may be primary or metastatic to solid or hollow intra-abdominal organs.
5. Subject must understand the investigational nature of this study and sign an Independent Ethics Committee/Institutional Review Board approved written informed consent.
6. Subject must have a skin prick test pre-operatively (at the time of the preoperative visit and after signed informed consent for entry into this clinical trial is given) to determine any sensitivity to fluorescein.

*Exclusion criteria:*

1. Uncontrolled intercurrent illness including, but not limited to, ongoing or active infection, symptomatic congestive heart failure, unstable angina pectoris, cardiac arrhythmia, or psychiatric illness/social situations.
2. Renal dysfunction as defined as a GFR < 45.
3. Liver dysfunction as defined by Child-Pugh score > 5, or LFT's 1.5x above normal range.
4. Any known allergy or prior reaction to fluorescein or a positive skin prick test to fluorescein.
5. Pregnant or nursing female subjects, determined preoperatively with a urine pregnancy test.
6. Unwilling or unable to follow protocol requirements.
7. Any condition which in the Investigators' opinion deems the patient unsuitable (e.g., abnormal EKG, including T wave inversion, elevated T waves, prolonged QRS interval, or conduction blocks) or that requires further work-up (including cardiac echo or stress test).
8. Any condition that excludes surgery as the standard of care (e.g. high disease burden where alternative treatments like systemic chemotherapy would be preferred).

Primary and Secondary Endpoints/Criteria for Evaluation:

*Primary endpoint:* A patient will be deemed a success if each of the following parameters were measured:

1. Identify tumor associated vessels and measure vessel diameters
2. Determine vessel density per 10x field
3. Visualize vital dyes within the tumor-associated vessels (fluorescein)
4. Calculate the blood flow velocity of the tumor-associated vessels and tissue penetration of fluorescein as a marker of vessel permeability.

Measurements will be obtained before and after any tumor vessel manipulation with either bolus fluids or vasopressors.

*Secondary endpoints:*

1. Post-operative comparison of the microvasculature of tumor with normal tissue (e.g. peritoneum) in each individual subject using vessel diameters, vessel density, detection of intravital dye and flow rates.

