The detection of blood flow parameters (including vessel diameter, flow rates, vessel density, and fluorescent markers of tissue diffusion) in deep space solid tumors of patients may have utility in characterizing the clinical response of these patients to systemic therapies. In addition, because many of these patients require intraoperative fluid boluses and vasopressor support, both of which are known to alter blood flow dynamics, the use of real time HIVM may reveal the ability to control tumor-associated vessels. It is anticipated that this approach has the potential to generate a more complete picture of the tumor-associated locoregional vasculature. The investigation of tumor-associated vessels in real time may lead to a better understanding of factors influencing systemic drug efficacy. Reflective of the study's two specific aims, our approach has the strong potential to expand upon novel tumor imaging techniques and not only form a directly observed basis of the tumor vasculature as a barrier to systemic drug efficacy in humans, but also establish a rationale means to overcome this barrier through standard intraoperative practice.

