Use of fluorescein sodium may be contraindicated in patients with history of allergic hypersensitivity to fluorescein. Although generally considered safe for patients receiving dialysis, one manufacturer of fluorescein suggests using half the normal dose in dialyzed patients.[22] There are no known risks or adverse reactions associated with pregnancy, but most practitioners avoid performing fluorescein angiography in pregnant women, especially in their first trimester.[23-25]

Historically, adverse reactions occur in 5% - 10% of patients and range from mild to severe.[27-32] Anecdotal evidence suggests a lower incidence of reaction in recent years and the first large study conducted in over a decade seems to confirm that, reporting a frequency of adverse reaction of just over 1%. [33] Continued improvements in manufacturing processes and implementation of tighter pharmacopeial standards are credited with this reduction and may lead to lower rates of reaction in the future.[34]

Transient nausea and occasional vomiting are the most common reactions and require no treatment. These mild reactions typically occur 30 – 60 seconds after injection and last for about 1 to 2 minutes. Fortunately, they seldom compromise the diagnostic quality of the angiogram. The incidence of nausea and vomiting seems to be related to the volume of dye and rate of injection. A relatively slow rate of injection often reduces or eliminates this type of reaction but can adversely affect image quality and alter arm-to-retina circulation times. Premedication with promethazine hydrochloride or prochlorperazine may prevent or lessen the severity of nausea and vomiting in patients with a history of previous reactions to fluorescein, but is rarely needed and one study noted a higher frequency of these reactions in patients that had been premedicated.[30] Some patients report a strong taste sensation or hypersalivation following injection of fluorescein.

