Moderate reactions occur less frequently, affecting less than 2% of patients that undergo angiography. Allergic reactions such as pruritus or urticaria can be treated with antihistamines, but any patient who experiences these symptoms should be observed carefully for the possible development of anaphylaxis. The advisability of performing angiograms in patients with a history of allergic reaction to fluorescein should be considered carefully, as allergic sensitization to the dye can increase with each subsequent use. Patients with previous history of mild allergic reaction to fluorescein can be pre-treated with an antihistamine, such as diphenhydramine, 30 - 40 minutes prior to any subsequent angiograms to limit allergic response, although this may not prevent serious reactions.[35]

More severe reactions are rare, but include laryngeal edema, bronchospasm, anaphylaxis, tonic-clonic seizure, myocardial infarction, and cardiac arrest.[36-40] The overall risk of death from fluorescein angiography has been reported as 1 in 222,000 due to anaphylaxis.[30] Although life-threatening reactions during angiography are rare, angiographic facilities and personnel should be properly equipped and prepared to manage serious reactions to the procedure. A resuscitative crash cart and appropriate agents to treat severe reactions should be readily available including epinephrine for intravenous or intramuscular use, soluble corticosteroids, aminophylline for intravenous use, oxygen, and airway instrumentation. It is generally recommended that a physician be present or available during angiographic procedures.

Extravasation of fluorescein dye during the injection can be a serious complication of angiography. With a pH of 8 to 9.8, fluorescein infiltration can be quite painful. If fluorescein dye extravasates, cold compresses should be placed on the affected area for 5 to 10 minutes, and the patient should be reassessed until edema, pain, and redness resolve. Serious complications are more likely to occur when large amounts of dye extravasate. Sloughing of the skin, localized

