1-2 mL of 10 or 25% fluorescein will be injected intravenously and observation will continue until loss of fluorescence over 2-4 areas of both grossly normal and tumor tissue. IVM is continuously performed at the time the fluorescent agent is injected and video is recorded in real-time. The fluorescein is almost immediately visible within the microscopic field, and the vessels are quickly outlined in great detail. The fluorescence lasts for a few minutes (2-3 minutes) and then either fades or begins to permeate through the tissue. The extravasation of dye will be determined by visualizing fluorescence outside of the defined vessels for a total time of 5 minutes. The distance from the vessels will be measured, recorded, and expressed as a function of time (extravasation rate) in an analysis performed off-line from the digitally recorded video. On average, the total observation time per field is 1-2 minutes.

During the course of the surgery, if fluid boluses and/or vasopressors (e.g. vasopressin and/or phenylephrine) are required and administered to maintain blood pressure during the resection, another round of IVM observations will be performed with a second dose of 1-2 mL of fluorescein. Communication with anesthesia will indicate when fluid boluses and/or vasopressors are administered, in order to coordinate the observation.

At the completion of the entire observation period, the microscope will be removed and sterilized between uses. This would complete the observation period, which is anticipated to take 10 – 12 minutes total time. The observation will take place during the course of standard surgery and is not anticipated to delay or lengthen the duration of the procedure. In fact, during this observation period, other portions of the surgical procedure will be performed, including pathologic biopsy assessment, margin assessment, intra-abdominal irrigation, drain placement and securement, implantation of hemostatic agents (Surgicel, Tissell spray, GelFoam, etc), or in the case of more than one tumor or satellite tumors, additional dissection of the remaining tumors. The patient will recover in the PACU per standard protocol. The patient will be monitored for any allergic reactions and/or side effects to fluorescein administration and treated appropriately as described in previous sections.

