## 14 APPENDICES

### Appendix A: Fluorescein Drug Package Insert.

- ▶ AK-FLUOR® (fluorescein injection, USP) is a sterile solution for use intravenously as a diagnostic aid
- ▶ Indicated in diagnostic fluorescein angiography or angioscopy of the retina and iris vasculature
- ▶ Meets strict USP quality standards
- ▶ AK-FLUOR® is contraindicated in patients with known hypersensitivity to fluorescein sodium or any other ingredients in this product
- ▶ Rare cases of death due to anaphylaxis have been reported [see *Warnings and Precautions (5.1)* and *Adverse Reactions (6.2)*]
- ▶ Available direct or through your authorized wholesaler or distributor

AK-FLUOR® (fluorescein injection, USP)		PRESERVATIVE FREE	RSS Barcoded	UPC Barcoded
NDC #	DESCRIPTION	SIZE	UNIT OF SALE	ORANGE BOOK CODE
17478-253-10	10% Single-dose Vial	5 mL	12	AP
17478-250-20	25% Single-dose Vial	2 mL	12	AP
EACH mL CONTAINS:				
ACTIVE:	17478-253-10: Fluorescein Sodium (equivalent to Fluorescein 10% w/v, 100 mg/mL); 17478-250-20: Fluorescein Sodium (equivalent to Fluorescein 25% w/v, 250 mg/mL);			
PRESERVATIVE:	None;			
INACTIVES:	Sodium Hydroxide and/or Hydrochloric Acid may be used to adjust pH (8.3 to 9.8), and Water for Injection.			
STORAGE:	Store at 20° to 25°C (68° to 77°F). Do not freeze.			
NDC #	CARDINAL	AMERISOURCEBERGEN	MCKESSON	MORRIS DICKSON
17478-253-10	2119436	861-005	2772069	084699
17478-250-20	2119444	089-829	1257831	TBA

To order products call [contact] or [contact] • [www.akorn.com](http://www.akorn.com)  
NOT FOR PRESCRIBING PURPOSES. PLEASE REFER TO PACKAGE INSERT FOR FULL PRESCRIBING INFORMATION.

[figure not shown]
[name]

P343 Rev. 10/13

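### The synopsis objective counts measurements after fluid or a vasopressor as a fifth success item, while the endpoint and Section 9 use four, so a patient without a usable second round is scored two ways; Section 4.2 also sets no hold on the second dye dose (minor).

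*Combined protocol and SAP*

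**What the plan says.** **Success.** The synopsis, under primary objectives, defines a successful observation by five items, each of which must be completed. The fifth is: "Obtain these vessel parameters after administration of an IV fluid bolus and/or vasopressor administration". The study design paragraph of the synopsis then says that if Part 1 is not met, the primary objective is not technically feasible and the study stops.

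Elsewhere the list has four items. The primary endpoint in the synopsis and in Section 3.3 begins "A patient will be deemed a success if each of the following parameters were measured" and numbers four parameters. Section 3.1 restates the objective with four. Section 9 calls the method feasible if at least seven of ten patients meet four criteria. An unnumbered sentence below the endpoint list says that measurements are taken before and after fluid or vasopressor manipulation.

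Section 4.2 replaces patients lost to microscope faults, or to events unrelated to the intervention that end the surgery. It keeps patients who receive no vasopressor, because their data serve Aim 1.

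**Second dose.** When fluid or a vasopressor is needed to maintain blood pressure, Section 4.2 says that "another round of IVM observations will be performed with a second dose of 1-2 mL of fluorescein". The same section says that patients are monitored for reactions and treated. Section 5.2 excludes anyone with a known allergy or prior reaction. Section 1.1.2 warns that "allergic sensitization to the dye can increase with each subsequent use", and the product sheet in Appendix A says the dye is "contraindicated in patients with known hypersensitivity to fluorescein sodium or any other ingredients in this product".

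**The concern.** The two lists cannot both be applied to a patient who completes items 1 to 4 and then has no usable second round. The round may be missing because the second dose was withheld, because the surgery left no opportunity, or because the video could not be read. The synopsis objective scores that patient a failure; Section 9 scores the same patient a success. Part 1 has ten patients and a threshold of seven, so one patient can decide whether the other 40 are enrolled.

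The safety point is smaller. Someone with a prior reaction could not enter the study, yet the dosing step does not say that a reaction to the first dose cancels the second. The Section 1 background says that "many of these patients require intraoperative fluid boluses and vasopressor support", so a second dose will be common.

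**Working it through.** **1. Scoring one patient under each text.** Take a patient with items 1 to 4 obtained on the first dose, then given fluid or a vasopressor, with no usable second round.

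- Synopsis primary objective (five items): item 5 missing, failure.
- Synopsis endpoint and Sections 3.1, 3.3 and 9 (four items): success.
- Section 4.2 replacement rule: covers neither a dye reaction nor a missing second round.
- Section 4.2 exception: covers only patients given no vasopressor.

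Item 5 depends on a second dose, because the parameters include dye within vessels and dye penetration, and Section 4.2 says fluorescence lasts 2 to 3 minutes. If items 1 to 4 were not met, both lists give failure and there is no split.

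**2. The plan's own figures.** Section 9 gives a 63%, 88% and 99% chance of declaring feasibility at true rates of 60%, 70% and 90%. The exact binomial P(X ≥ 7), X ~ Bin(10, p), gives 38.2%, 65.0% and 98.7%. Only the last agrees. The stated 63% matches a threshold of six at 60% (63.3%), and 88% matches a threshold of seven at 80% (87.9%). That is a separate matter; I use the recomputed values as the baseline.

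The synopsis also gives its own stopping count, three or more patients, which differs from Section 9 at exactly seven successes. That too is separate. I use seven of ten throughout, so that only the definition of success varies.

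**3. How often a reaction could remove the second round.** Section 1.1.2 says: "Moderate reactions occur less frequently, affecting less than 2% of patients that undergo angiography". Assumptions: suspected allergic reactions stay within this class, and between half and all of these patients also receive fluid or a vasopressor. The share with a withheld second dose is then w = 0.01 to 0.02 as a ceiling, before any benefit from skin-prick screening.

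- Expected at w = 0.02: 10 × 0.02 = 0.2 patients in Part 1; 50 × 0.02 = 1 in the whole study.
- At least one in ten: 1 − 0.98^10 = 0.183; at w = 0.01, 1 − 0.99^10 = 0.096.

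**4. Effect on Part 1 if the five-item list were used.** Let p be the chance of meeting items 1 to 4 and w the chance of no usable second round, independent of p. The four-item pass probability is P(Bin(10, p) ≥ 7); the five-item one is P(Bin(10, p(1 − w)) ≥ 7).

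| w (assumed) | p = 0.70: four vs five items | p = 0.90: four vs five items |
|---|---|---|
| 0.01 | 0.6496 vs 0.6308 (1.9 points) | 0.9872 vs 0.9828 (0.4 points) |
| 0.02 | 0.6496 vs 0.6119 (3.8 points) | 0.9872 vs 0.9774 (1.0 point) |
| 0.05 | 0.6496 vs 0.5547 (9.5 points) | 0.9872 vs 0.9552 (3.2 points) |
| 0.10 | 0.6496 vs 0.4600 (19.0 points) | 0.9872 vs 0.8961 (9.1 points) |

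The first two rows are the dye-reaction case. The last two only illustrate second rounds missing for other reasons. The documents give no rate for those, so I claim no size for them.

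**The case against.** **On scoring.** The four-item reading is the better supported one. The endpoint is the text that says when a patient is deemed a success, and Section 9 holds the count of seven and lists four criteria beneath it. The last paragraph of Section 4.2, describing how success will be determined from saved data, mentions no post-fluid measurement. A statistician following Section 9 would not use item 5. This stands, and it is why the point is minor. It does not remove the conflict, because the synopsis ties stopping to an objective that includes item 5. The before-and-after sentence could be read as narrowing the gap, but it is not a numbered criterion and is absent from Section 9.

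**On the second dose.** A reader might infer that the protocol orders re-exposure of a patient who has just reacted. The documents do not support that. The trigger is routine blood-pressure support during resection, reactions are monitored and treated, and nothing forbids withholding. Clinicians would very probably withhold. Section 1.1.2 also allows that patients with an earlier mild allergic reaction can be pre-treated before a later angiogram, so its advice is careful consideration rather than an absolute bar. The Data Safety Monitoring Plan is filed with the IRB and the full package insert is not reproduced, so a hold rule may exist outside these pages. What remains is an unconditional instruction beside an entry exclusion and a contraindication that point the other way.

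**Conclusion.** The point holds as a minor inconsistency with a simple correction. The synopsis objective and the four-item texts disagree on any patient who meets items 1 to 4 without a usable second round. The missing hold on the second dose is a rare, secondary safety gap.

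For dye reactions, the effect on the Part 1 decision is at most about 4 points at a true rate of 70% and about 1 point at 90%. These are ceilings: they take the upper limit for moderate reactions, assume every such patient receives fluid or a vasopressor, and apply only if the synopsis list is used for scoring. Section 1.1.2 also cites a later large study with all adverse reactions at just over 1%, which suggests a smaller effect.

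A reader might infer that the Part 1 decision is in real danger. The documents do not support that, because Section 9, which states the go rule, uses the four-item list.

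**What to change.** 1. In the synopsis, remove item 5 from the success list and add: *Part 1 success is judged on criteria 1-4 as in Section 9; post-fluid/vasopressor measurements serve Aim 2 only.* The sentence should not limit success to the first round. Sections 3 and 9 contain no such restriction, and it would turn a patient whose criteria were completed only in the second round into a failure.

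2. In Section 4.2, add: *No second fluorescein dose is given after a suspected allergic or hypersensitivity reaction to the first dose, or when the fluid or vasopressor is given to treat such a reaction.* The last clause rests on clinical inference: treating a reaction could itself satisfy the literal trigger. Transient nausea or vomiting alone would not invoke the rule.

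Cost: two sentences and one deleted item. At most about 1 of 50 patients loses the Aim 2 before/after comparison. The sample size, the seven-of-ten rule and the Section 9 analyses stay as they are.

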## SYNOPSIS: Intravital Microscopy (IVM) in Human Solid Tumors

PI: [name] [name]

Co-PI: [name]

[name]

[name]

[name]

[name]

[name]

Statistician: [name], MS

Study Center: Mayo Clinic Florida

Concept and Rationale: Intravital microscopy (IVM) allows real-time, direct visualization of microscopic blood vessels and calculation of blood flow. Our group has used IVM in mouse models to characterize aberrant blood vessel structure surrounding tumor implants and the associated impaired lymphocyte trafficking along these tortuous vessels.[1] These preclinical studies have been translated to human intravital microscopy (HIVM) in a pilot study that analyzed the tumor-associated microvasculature at primary melanomas.[2] The feasibility of HIVM was 90% at the primary tumor. As an extension of this completed trial, [name] had implemented an on-going clinical trial (NCT02857374, Intravital Microscopy in Identifying Tumor Vessels in Patients with Stage IB-IIIC Melanoma Undergoing Sentinel Lymph Node Biopsy) that investigates the role of IVM in analyzing the vessels associated with sentinel lymph nodes. In addition, with members of the multidisciplinary team listed, above, we have also implemented a trial in HIVM at Mayo Clinic Florida that investigates HIVM in patients with peritoneal carcinomatosis, NCT03517852 Intravital Microscopy (IVM) in Patients with Peritoneal Carcinomatosis (PC). This proposed trial at Mayo Clinic Florida will further determine the usefulness of IVM in human subjects, now applying it to patients with intra-abdominal or retroperitoneal tumors as well as study the effects of fluid shifts on the tumor blood flow in real time.

In this clinical trial proposal, the following aims will be addressed:

Aim 1: Determine the feasibility of HIVM in characterizing the tumor-associated vessels in patients with deep space solid tumors and correlate these findings with patient outcomes. We hypothesize that HIVM will be feasible in deep space solid tumors and function as a predictive biomarker for response to systemic therapy.

Aim 2: Determine the effects of dynamic control on tumor vessel blood flow during surgical resection. We will investigate whether we can reproduce enhanced tumor blood flow, established in our previous animal models, in human subjects using our dynamic control protocol (consisting of a fluid bolus and vasopressors, routinely given during the course of surgery).

Objectives:

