#### 4.2 STUDY METHODS

During the course of treatment for deep space solid tumors while the patient is under anesthesia, surgical resection will be performed. Approach to surgery may include open, laparoscopic, or robotic, as the HIVM microscope can be used through any of these approaches.

The IVM technology utilized at Mayo Clinic currently consists of a high resolution confocal endomicroscope (Appendix C). This apparatus has the ability to provide single cell resolution and high quality images of the microvasculature. While the typical application of this device is to investigate GI mucosal surfaces (i.e. esophagus or colon), it can be readily and easily applied to any surface. It can be sterilized via standard STERRAD techniques or used with a sterile sleeve in order to interface with the peritoneal surface, as currently used in NCT03517852: Intravital Microscopy (IVM) in Patients with Peritoneal Carcinomatosis (PC).

The microscope will be moved into position next to the OR table by the operating surgeon after the tumor is exposed. The microscope will be covered with a standard sterile drape similar to that used for cords associated with other intraoperative devices (NeoProbe or intraoperative ultrasound). The only exposed area will be the microscopic objective located at the tip of the endoscope, which will be made sterile along with the entire probe. This microscopic objective will come into close contact with the peritoneal surface for microscopic observation. Once the microscopic objective is in proper position, the epifluorescent light source will be turned on and digital video recording will commence. All video images will be captured to the hardware directly attached to the microscope (Appendix C). All data will be backed up on a password-protected hard drive in the Principal Investigator's laboratory.

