A matched analysis will be performed for observations of microvasculature between the tumor and normal tissue. For dichotomous variable comparisons between vessel structure (normal vs aberrant), vessel branching patterns (normal vs aberrant), or detection of intravital dye (present vs absent), a McNemar's test will be performed. For continuous variable comparisons between blood vessel density and average blood flow rate, a paired t test will be performed.

Associations between characteristics for the baseline (normal peritoneal microvasculature observed surrounding the tumor) and tumor itself will be depicted with graphics, correlations, and model results.

Similar analyses will be performed to compare baseline observations with those performed after fluid bolus and/or vasopressor administration.

Adverse event and complication rates will be described using upper one-sided 95% Clopper Pearson confidence limits.

Overall survival will be defined as the duration of time from diagnosis to time of death. Disease specific survival will be defined as the time from surgery to death due to recurrence. Overall survival and disease specific survival will be generated using standard Kaplan-Meier methodology.

A maximum of 50 subjects will be enrolled in this study (initially 10 to determine feasibility and then 40 additional subjects if deemed feasible). The accrual rate is estimated at 1-2 subjects per month, and the estimated study duration is 30 months (2.5 years).

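### The Aim 2 before/after comparison neither records nor allows for surgical division of the tumor's blood supply between the two imaging rounds

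*Combined protocol and SAP*

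**What the plan says.** - **Aim (Synopsis, Aim 2):** "Determine the effects of dynamic control on tumor vessel blood flow during surgical resection". The stated interest is whether the flow enhancement seen in animals can be reproduced with a fluid bolus and vasopressors.
- **First round (Section 4.2):** "The microscope will be moved into position next to the OR table by the operating surgeon after the tumor is exposed". Tumor exposure is the only anchor.
- **Second round (Section 4.2):** it takes place if fluid boluses or vasopressors "are required and administered to maintain blood pressure during the resection, another round of IVM observations will be performed with a second dose". The only timing control is this: "Communication with anesthesia will indicate when fluid boluses and/or vasopressors are administered, in order to coordinate the observation".
- **Concurrent steps (Section 4.2):** to support the expectation of no added operating time, the text says that during the observation period "other portions of the surgical procedure will be performed, including pathologic biopsy assessment, margin assessment, intra-abdominal irrigation, drain placement and securement". It goes on to hemostatic agents, "or in the case of more than one tumor or satellite tumors, additional dissection of the remaining tumors".
- **Analysis (Section 9):** "Similar analyses will be performed to compare baseline observations with those performed after fluid bolus and/or vasopressor administration". The analyses referred to are McNemar's test and the paired t test set out for tumor versus normal tissue.
- **Control (Section 9.1):** the study is nonrandomized, and no untreated second round is planned.

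**The concern.** A paired before/after difference can be read as the effect of the agent only if nothing else that drives tumor flow changed between the two readings. Here the second reading always comes later in the same operation, and the operation is one that removes the tumor. If a vessel supplying the imaged tumor is divided between rounds, flow falls for a surgical reason, and the plan enters that fall as the response to fluid or vasopressor.

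Aim 2 looks for an increase, so such a loss works against it: a real increase could be hidden or reversed, and an agent with no effect could appear to reduce flow. The plan does not ask for supply status or surgical stage at each round, so affected pairs could not be reliably identified at analysis.

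**Working it through.** The plan gives no sample size, effect size, standard deviation or significance level for the before/after contrast, so there is no figure of its own to reproduce. Four checks were made.

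**1. The text side by side.** The first round depends on tumor exposure. The second depends on a hemodynamic event at any point in the resection. Neither Section 4.2 nor Section 9 requires the tumor's supply to be unchanged between rounds, and neither asks for ligation status, surgical stage or the time between rounds. The before/after note in Section 3.3 refers only to fluids and vasopressors, not to surgical changes. Of the concurrent steps, margin assessment, irrigation, drains and hemostatic agents ordinarily come late in a resection; biopsy assessment and dissection of further tumors need not. That ordering is general surgical knowledge, not protocol text. It is enough to show that the list and the imaging of an exposed, perfused tumor need to be reconciled.

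**2. Do both rounds fit one short window?** Section 4.2 gives 2-4 areas of normal and tumor tissue, 1-2 minutes per field, and 10-12 minutes in total. Time per round = number of areas x minutes per field.
- If 2-4 areas of each tissue are meant: from 4 x 1 = 4 to 8 x 2 = 16 minutes per round, so 8 to 32 minutes for two rounds.
- If 2-4 areas in all are meant: from 2 x 1 = 2 to 4 x 2 = 8 minutes per round, so 4 to 16 minutes for two rounds.

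The stated total therefore does not establish that both rounds are close together. The second also waits for a clinical event whose timing is not set.

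**3. Effect on the mean change (all inputs assumed).** Let f be the share of second rounds taken after division of the supply, with a change of +20% in perfused tumors and -60% after division:

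mean change = (1 - f) x 20% - f x 60%

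- f = 0.10: 18 - 6 = +12%
- f = 0.25: 15 - 15 = 0%
- f = 0.40: 12 - 24 = -12%

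If division abolishes flow (-100%):
- f = 0.10: 18 - 10 = +8%
- f = 0.25: 15 - 25 = -10%
- f = 0.40: 12 - 40 = -28%

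**4. Effect on the paired t test (all inputs assumed).** The test was simulated 20,000 times per setting at a two-sided 5% level. Paired differences had SD 1, and a share f of pairs lost 1 SD of flow for surgical reasons. Each cell gives the rejection rate with no agent effect, then the power to show an increase when the agent truly adds 0.5 SD. The f = 0 row is the nominal level and the exact power.

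| Share f | 20 pairs | 30 pairs | 50 pairs |
|---|---|---|---|
| 0 | 5% / 56.4% | 5% / 75.4% | 5% / 93.4% |
| 0.10 | 6.4% / 37.2% | 7.8% / 52.4% | 10.2% / 75.8% |
| 0.25 | 16.1% / 16.7% | 22.9% / 23.0% | 35.9% / 35.5% |
| 0.50 | 47.2% / 2.6% | 65.5% / 2.5% | 87.4% / 2.5% |

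The number of pairs is also an assumption. The plan caps enrollment at 50 but does not say how many patients will have a second round.

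**The case against.** The strongest reply has five parts.

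- **Opportunistic timing is inherent.** The agents are given only as routine care, and the before/after comparison is one unpowered sentence in Section 9 with no matching objective in Section 3. This stands and lowers the severity. It does not remove the problem, because Aim 2 is a stated aim and the comparison is planned.
- **The rounds may be close together.** Section 4.2 describes a single observation period of 10-12 minutes. This is a fair reading but not a conclusive one, as the time arithmetic shows.
- **Gross loss of flow would be visible, and raw video is kept.** This helps for complete loss. It does not separate partial loss from an agent effect.
- **Normal tissue is imaged too.** Section 9 plans no comparison of tumor change with normal-tissue change, and normal peritoneum would not share a loss of supply specific to the tumor.
- **Other things also change between rounds,** such as blood pressure, time and anesthesia. This is true, and restricting the pairs will not cure it. Surgical division of supply is nonetheless a source that can be recorded cheaply.

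Three stronger readings are tempting but unsupported:

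- A reader might infer that agent need rises as vessels are divided, so that second rounds are systematically linked to lost inflow. No section says so; the need could arise at any stage.
- A reader might infer that no perfused tumor could be imaged during the listed steps. The list includes biopsy assessment and dissection of further tumors, and with several lesions one may be imaged while another's margins are assessed.
- A reader might infer that late first rounds will cause primary-endpoint failures. The first round is anchored to tumor exposure, nothing directs it to be late, and none of the four Part I criteria in Section 9 is a before/after change.

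**Conclusion.** The point holds as a should-fix. As written, the plan can attribute surgical loss of tumor inflow to fluid or vasopressor, because second rounds enter an uncontrolled paired comparison with no record of supply status and no term for surgical stage. The gap lies mainly in the second round.

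The likely direction, against the increase that Aim 2 looks for, follows from loss of inflow lowering flow. The frequency and size are unknown. The percentages, shares and standardized shifts above are illustrations and say nothing about how often this would occur in this trial. The view that most of the listed concurrent steps come late rests on general surgical knowledge.

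**What to change.** 1. **Section 4.2, data collection.** For each imaging round, record the clock time, the time of each bolus or vasopressor, and whether any vessel supplying the imaged tumor had been divided. This is recording only; it changes neither the operation nor fluid and vasopressor care.
2. **Section 9, analysis set.** Base the main before/after comparison on pairs in which tumor inflow was unchanged between rounds. Report the remaining pairs separately as descriptive data.
3. **Section 4.2, text.** Reconcile the list of concurrent steps, and the no-added-time statement that rests on it, with imaging of a tumor that is still perfused.

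The cost is a few fields taken from the operative and anesthesia records, one analysis-set sentence, and fewer pairs in the Aim 2 comparison. The comparison remains uncontrolled for other changes during surgery, and the report should say so.
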